6.2 Secondary Endpoints

Secondary endpoints will include the following:

- The mean pain improvement at time 15, 30, 60, 120, 150 and 180 minutes (using same test as primary end point).

- Difference in proportion of patients with adverse events, who experience serious adverse events, require medication to treat adverse events, report insufficient pain relief, require naloxone, have a change in disposition, and a missed diagnosis will be evaluated using a Chi-Square test with an alpha level of 0.05.
- Proportion of patients who prefer to receive the same drug at a future visit will be compared as proportions using a Chi-Square test with an alpha level of 0.05.

8.1 Statistical Methods

6.2.1 Baseline Data

Baseline and demographic characteristics and medical history will be summarized by standard descriptive summaries. Mean and standard deviation will be recorded for age. Percentages will be recorded for categorical variables.

6.2.2 Efficacy Analysis

The primary outcome will be assessed using a two-tailed t-test using an alpha level of 0.05. A 95% confidence interval will be recorded for each mean. The same test will be used for all numerical pain outcomes. All other tests will use a chi-square test with an alpha level of 0.05 and confidence interval of 95%.

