4.4 Missed Measurements

- In the event one of the numerical secondary outcomes is missed, an average of the measurements before and after will be used as a substitute. Any other data point will not be substituted and recorded as missed. These, in addition to allowing up to a 15 minute delay in measuring a variable, will not be counted as protocol deviations.

- If a patient leaves the emergency department prior to 180 minutes, they will no longer be followed for timed measurements. They will still be contacted for the follow up portion of the study.

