6 STATISTICAL CONSIDERATIONS

6.1 Primary Endpoint

The primary endpoint is mean improvement in pain score, defined as the difference between pain score at the beginning of the study drug infusion (time zero) and 90 minutes after the study drug was administered (time zero). The mean pain improvement will be compared between each study drug using a two tailed t-test with an alpha level of 0.05 and confidence interval.

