9.4.2 Risk Assessment

Hydromorphone has been well studied and there are no specific risks for using it in this clinical trial that are unique to the risks encountered in routine clinical care.

Lidocaine is FDA approved for ventricular arrhythmias at an initial dose of 1.5 mg/kg (IV push) and up to three repeat doses of 0.5 mg/kg at intervals of 5 minutes after the initial bolus. We are using a dose of 2 mg/kg over 5 minutes and for the indication of abdominal pain. While the initial dose is marginally higher, it will be given over 5 minutes which will improve the safety profile compared to giving it as an IV push. Additionally, the cumulative dose will be less than the maximum dose available for an FDA approved use.

Side effects from lidocaine will be prevented by eliminating subjects most likely to experience them. This is part of the exclusion criteria. Lidocaine is metabolized by the liver and cleared from the body by the kidneys, so any patient with significant renal or hepatic impairment will be excluded. Lidocaine can also affect the heart, so any patient with an abnormal EKG (defined as any interval abnormality) will be excluded. Geriatric patients can be more sensitive to intravenous lidocaine, so patients aged 65 and older will be excluded.

Patients will be on a cardiac monitor throughout the study (unless taken away for imaging but usually this would happen after at least 30 minutes from the patient receiving the study drug), thus allowing the treatment team to quickly identify any arrhythmia from lidocaine. If the patient is off of a cardiac monitor, they will continue to be closely supervised. If a patient is eligible for discharge prior to 180 minutes of cardiac monitoring, they will be asked to remain in the department until 180 minutes but will not be placed on a hold if they decide to leave. They will not be excluded from the study if they elect to leave before 180 minutes of monitoring.

Finally, lidocaine toxicity has a typical course, generally starting with perioral anesthesia then moving on to feeling light headed or having mildly slurred speech with increased toxicity. These potential side effects will be explained to the patient so if they experience them, the infusion can be stopped and once the symptoms clear, started again but over a period of 10 minutes, not 5 minutes.

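### The primary t-test drops patients without a 90-minute score and uses baseline only by subtraction; a baseline-adjusted repeated-measures model is a cheap, modest improvement

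*Combined protocol and SAP*

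**What the plan says.** Section 6.1 defines the primary endpoint as the change in pain from time zero to 90 minutes and says: "The mean pain improvement will be compared between each study drug using a two tailed t-test with an alpha level of 0.05". Section 6.2.2 repeats this: "The primary outcome will be assessed using a two-tailed t-test using an alpha level of 0.05". Section 6.2 applies the same test separately at the six other post-dose times. No covariate and no repeated-measures model is named. Section 6.1 mentions a confidence interval without saying of what; section 6.2.2 says: "A 95% confidence interval will be recorded for each mean".

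Section 4.4 has two rules for missed values. If "one of the numerical secondary outcomes is missed, an average of the measurements before and after will be used as a substitute". Otherwise: "Any other data point will not be substituted and recorded as missed". The 90-minute score is the primary outcome and is not in the section 6.2 list, so the second rule governs it. The same section adds: "If a patient leaves the emergency department prior to 180 minutes, they will no longer be followed for timed measurements".

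Some provisions limit the loss. Section 9.4.2 says of patients ready for early discharge that "they will be asked to remain in the department until 180 minutes but will not be placed on a hold", and keeps those who go in the study. Section 4.2 tolerates a 15-minute delay for each score. Section 6.3 inflates the sample for a 10% loss. The synopsis gives the analysis principle as intention to treat.

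**The concern.** A patient who misses the 90-minute reading, or leaves before it, has no primary value and drops out of the primary test. That patient may still have pain scores at 15, 30 and 60 minutes, and these carry information about the 90-minute score. If the chance of a missing score depends on pain, the patients who remain are a selected group, and the estimate can be off although data that could reduce the error are on file.

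Subtracting baseline also fixes its slope at 1. Estimating the slope has no large-sample variance penalty and may gain precision.

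Direction matters too. Sections 2 and 2.1 aim to show equal efficacy, so any pull towards no difference favours the conclusion the trial hopes for.

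A smaller point concerns secondary results only. Averaging the neighbouring scores mixes the pre-dose score into a missed 15-minute value, and it cannot be done at 180 minutes because no later timed score exists.

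**Working it through.** **1. The plan's own sample size (section 6.3).** Inputs: two-sided alpha 0.05, power 80%, SD 3, difference 1.3.

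- Normal approximation: n = 2(1.960 + 0.842)² × 3² / 1.3² = 83.6, so 84 per arm.
- Exact t calculation: 84 per arm gives 79.7% power and 85 gives 80.2%, which reproduces the stated 85.
- 2 × 85 × 1.10 = 187, as stated.
- With 10% of 187 lost, 187 × 0.90 / 2 = 84.15 per arm remain, and power is still about 80%. The inflation therefore already pays for the lost power.

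**2. Precision from baseline adjustment.** The documents give neither the baseline SD (s0) nor the correlation (ρ) between baseline and 90-minute scores. Assumed: s0 of 1 to 2, ρ of 0.3 to 0.5, and 90-minute SD s1 = 3.

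Variance ratio (adjusted / change score) = s1²(1 − ρ²) / (s0² + s1² − 2ρ·s0·s1)

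| s0 | ρ = 0.3 | ρ = 0.4 | ρ = 0.5 |
|---|---|---|---|
| 1 | 0.999 | 0.995 | 0.964 |
| 1.5 | 0.958 | 0.988 | 1.000 |
| 2 | 0.871 | 0.922 | 0.964 |

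The median is 0.964, and seven of nine are above 0.95. The variance reduction is thus 0 to 13%, median 3.6%. Power at 85 per arm, using SD 3√ratio, goes from 80.2% to 81.6% at the median and 85.3% at most. If baseline varied as much as the 90-minute score the gain would be larger. Entry requires pain severe enough for intravenous narcotics, which may narrow the baseline spread.

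**3. Precision from the earlier scores.** Let r be the correlation of the earlier scores with the 90-minute score (assumed). Effective n = 1 / [(1 − r²)/84.15 + r²/93.5]. For r = 0.5 to 0.9 this gives 86.3 to 91.6 per arm. Power, by the normal approximation, is 81.2% to 83.5%, against 80.3% for the t-test at 10% missing.

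**4. Bias, by simulation.** 4,000 trials per setting, 93 per arm. Assumed: baseline SD 1.5, post-dose SD 3, baseline correlation 0.4, correlation 0.8 between adjacent post-dose scores. The model was fitted by maximum likelihood with unstructured covariance.

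| Missingness follows | True difference | 10% missing | 5% missing | 3% missing |
|---|---|---|---|---|
| 60-minute score, one arm, log-odds 1 per SD | 0 | bias 0.16 | bias 0.09 | bias 0.05 |
| 60-minute score, one arm, log-odds 0.5 per SD | 0 | bias 0.09 | bias 0.04 | bias 0.03 |
| 60-minute score, same rule in both arms | 0 | none within error | none within error | not run |
| 60-minute score, same rule in both arms | 1.3 | estimate 1.24 | estimate 1.26 | estimate 1.28 |
| Unseen 90-minute score, one arm | 0 | bias 0.22 | bias 0.11 | not run |

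These are t-test results; repeat runs agreed within about 0.01. The repeated-measures model was within 0.01 of the truth in the one-arm log-odds-1 runs on the 60-minute score, and gave 1.29 to 1.30 where the true difference was 1.3. When missingness followed the unseen 90-minute score, the model's bias was 0.10 at 10% and 0.05 at 5%.

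For scale, 0.16, 0.09 and 0.05 are 12%, 7% and 4% of 1.3. The plan's standard error is 3√(2/85) = 0.46; in the simulation it is about 0.42, because the change score there has SD √(1.5² + 3² − 2 × 0.4 × 1.5 × 3) = 2.77. In the first row the t-test's false-positive rate was 6.2% at 10% missing and within simulation error of 5% at the lower shares.

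**The case against.** The strongest reply is that nothing here is shown to go wrong. The t-test is valid with complete data. Patient, nurse and physician are blinded (section 3.1), patients are asked to stay well past 90 minutes, late readings are accepted, and the sample already allows for 10% loss. Dependence on pain in one arm only, at log-odds 1 per SD, is an upper-end case, and the bias roughly halves at 0.5. The model's near-zero bias owes much to a simulation that meets its assumptions: when missingness follows the unseen score, it keeps 0.095 / 0.218 = 44% of the t-test's bias. Scores were simulated as normal and not on a bounded 1-10 scale, rescue medication was left out, and Kenward-Roger degrees of freedom were not run.

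Most of this stands, and it limits the point to a cheap improvement. A reader might infer that the primary analysis is biased, that the trial is short of patients, or that no rule exists for a missed primary score. The documents support none of these: they do not say how many 90-minute scores will be missing or why, the inflation covers the power, and section 4.4 does state a rule. Nor does keeping early leavers in the study contradict that rule, since section 4.4 keeps them for the telephone follow-up.

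Blinding does not answer everything. If patients with more relief leave more often under the same rule in both arms, and the drugs differ, the more effective arm loses more of them. Equal behaviour in both arms therefore removes the bias only when the true difference is zero.

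**Conclusion.** The point holds as a cheap improvement of modest size. The planned test discards recorded information that bears on the primary outcome.

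The precision gain is a point or two of power in most assumed settings. The bias ranges from nothing to about 0.16 points at 10% missing when the 60-minute score drives it, and somewhat more if the unseen score does. In the same-rule case the shrinkage is 1.30 − 1.24 = 0.06 points at 10% missing. That is towards the equality the trial hopes to show, but it is too small by itself to support a claim that the design would produce a false finding of equality.

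All of these sizes rest on assumed SDs, correlations, missing shares and dropout mechanisms. The 10% loss in section 6.3 is not broken down and may include withdrawals, whose data the model could not use. If few 90-minute scores are missing, the two analyses will nearly agree. The defect in the averaging rule is certain, but it touches secondary results only.

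**What to change.** - **Sections 6.1, 6.2 and 6.2.2:** pre-specify a mixed model for repeated measures on all scheduled post-dose pain scores, with patients in their assigned arm. Fixed effects: baseline, arm, time, baseline-by-time and arm-by-time. Use unstructured covariance with a fixed fallback order (for example heterogeneous Toeplitz, then heterogeneous first-order autoregressive) and a small-sample degrees-of-freedom method such as Kenward-Roger.
- **Reporting:** give the 90-minute arm difference with its 95% confidence interval, and take the other times from the same model.
- **Section 6.4:** use the same model and fallback at the interim. With about 94 / 2 = 47 per arm, the unstructured fit converged in all 4,000 runs at 5% and at 10% missing.
- **Sensitivity:** keep the change-score t-test, and add one missing-not-at-random analysis that shifts missing 90-minute scores by arm.
- **Section 4.4:** delete the averaging rule and say that missed pain scores are handled by the model.

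ANCOVA of the 90-minute score on arm and baseline is the minimum, for precision only. It does not recover the dropped patients or reduce the bias (0.172 against 0.160 for the t-test at 10% missing in one arm).

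The cost is plan wording and more analysis work, with no new data and no change in sample size. The downside is that the model assumes missingness is explained by observed scores, hence the sensitivity analysis. It does not settle withdrawn patients' data (section 4.6.1) or scores taken after rescue medication (section 4.5); both need separate text on how they are analysed.

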6.2.3 Pharmacokinetic Analysis

No pharmacokinetic analysis will take place.

6.2.4 Safety Analysis

All subjects entered into the study will be included in the safety analysis, with the exception of those who wish to withdraw from the study. The frequencies of AEs by type will be summarized. Serious adverse events will be described in detail. Incidence of all safety outcomes will be summarized along with the corresponding exact binomial 95% two-sided confidence intervals.

6.3 Sample Size and Power

Our sample size was calculated using an alpha level of 0.05, beta level of 80%, standard deviation (SD) of 3 (previous research showed a SD of 3.1 for IV lidocaine and 2.9 for hydromorphone), and a minimal importance clinical difference in pain score of 1.3. This resulted in 85 patients per arm. Anticipating a loss of 10% of patients per arm, our final sample size was 187.

6.4 Interim Analysis

The decision to stop the study for efficacy or safety will be primarily determined by the Data Safety Monitoring Board (DSMB). After 94 patients have been enrolled, they will complete an interim analysis.

The stopping boundary for efficacy will be met if the P-value using a t-test for the difference between groups in the primary outcome is 0.001 or less. Using this conservative

Haybittle-Peto boundary ($P \leq 0.001$) will allow the final analysis to be performed using an unchanged level of significance.

The stopping boundary for safety will be met if the P-value using a chi-square test for the difference between groups in the serious adverse event outcome is 0.025 or less.

7 STUDY MEDICATION (DRUG, DEVICE, OR OTHER STUDY INTERVENTION)

7.1 Description

Study drugs will include lidocaine and hydromorphone.

7.1.1 Packaging

Study drugs will be prepared by the research pharmacist who will place each drug in a non-descriptive 100cc bag of saline. Both medications are clear and if placed side by side in a bag of saline, would be indistinguishable as the research staff will be blinded to medication assignment.

7.1.2 Labeling

Each study drug will be labeled with the standardized label below:

Header (**INVESTIGATIONAL MED**), Patient name, age, medical record number, location, tube number, order number, due time and date, drug name (INV lidocaine or hydromorphone in NaCL 0.9% 100 ml IVPB), intravenous, once, 100ml, infuse over: 5 minutes, time label printed, signature for preparer and checker, expiration, and “Caution: New Drug - Limited by Federal (or United States) law to investigational use

7.1.3 Dosing

Lidocaine will be dosed at 2 mg/kg. The patients recorded weight will be used. Hydromorphone will be dosed at 1 mg. Both drugs will be given over 5 minutes through an infusion pump.

The IV lidocaine solution that we are using for the Lidocaine component is premixed in 5% Dextrose. The appropriate amount based on milligrams will be removed from the Lidocaine and Dextrose 5% bag and added to a bag of 100 ml 0.9% Sodium Chloride. Prior to adding the lidocaine solution to the Sodium Chloride 100 ml bag, the volume equivalent to the amount to be added will be removed from the saline bag. The NDC for the 0.9% Sodium Chloride 100 ml is 0338-0049-18.

The expiration for prepared lidocaine and hydromorphone bags are 24 hours but will be given as quickly as possible after they are mixed, most likely in less than 30 minutes.

7.1.4 Treatment Compliance and Adherence

Not applicable.

7.1.5 Drug Accountability

A list of which drug each participant received will be maintained by the research pharmacist. It will only be made available to the DSMB by request and to the principal investigator after 187 patients have been recruited and their data has been recorded.

8 SAFETY MANAGEMENT

8.1 Clinical Adverse Events

Clinical adverse events (AEs) will be monitored throughout the study.

8.2 Adverse Event Reporting

Unanticipated problems related to the research involving risks to subjects or others that occur during the course of this study and SAEs will be reported to the IRB in accordance with IRB Attachment EEE: Prompt Reporting Guidelines. AEs that are not serious but that are notable and could involve risks to subjects will be summarized and submitted to the IRB at the time of continuing review. Abnormal blood work will only be reported as an adverse event if it was drawn after the patient received the study medication and is a departure from baseline lab work.

8.3 Definition of an Adverse Event

An adverse event is any untoward medical occurrence in a subject receiving a test article and which the occurrence does not necessarily have a causal relationship with the treatment. An adverse event can therefore be any unfavorable and unintended sign (including an abnormal laboratory finding), symptom, or disease temporally associated with the use of the test article, whether or not related to the product.

All AEs (including SAEs) will be noted in the study records and on the case report form with a full description including the nature, date and time of onset, determination of non-serious versus serious, intensity (mild, moderate, severe), duration, causality, and outcome of the event.

8.4 Definition of a Serious Adverse Event (SAE)

An SAE is any untoward medical occurrence that:

- results in death,
- is life-threatening,
- requires inpatient hospitalization or prolongation of existing hospitalization,
- results in a persistent or significant disability/incapacity, or
- is a congenital anomaly/birth defect.

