1.2.2.2 Clinical Studies in Adults

Below you will clinical human data in support of the use of intravenous lidocaine and at a dose of 2 mg/kg. This is directly from the IND application.

Lidocaine HCl is FDA approved for the treatment of ventricular arrhythmias in myocardial dysfunction and in cardiac surgery. The dose for that indication is 1.5 mg/kg, with repeat doses 0.5-0.75 mg/kg up to a total dose of 3 mg/kg over 15 minutes. Given that this indication is for the treatment of an arrhythmia, some may consider it unfair to compare the safety of that dose range for patients without a cardiac arrhythmia, since one of the most feared complications from intravenous lidocaine is an arrhythmia. To support the safety of our intended use, acute abdominal pain, we have conducted a literature of peer reviewed articles who have used lidocaine at a dose of 2 mg/kg for the treatment of pain, either in the operating room or in the emergency department.

Kasten et al. (19) investigated whether adding a 3 mg/kg dose of intravenous lidocaine with infusion of 0.05 mg/kg/min to a fentanyl infusion at 5mcg/kg/min would prevent hyperdynamic changes in patients undergoing cardiac surgery. Ten patients would ultimately receive lidocaine. This was a double blinded, randomized comparative efficacy trial. Prior to receiving either of these medications. The morning of the surgery, patients had received beta blockers, calcium channel blockers and nitrates. Forty five minutes prior to the surgery, patients received an intramuscular injection of morphine at 0.12 mg/kg and 2 mg of lorazepam. If there were increases in a patient's blood pressure or heart rate, pushes of fentanyl were given and if that was insufficient, patients received a nitroglycerin infusion and isoflurane until hemodynamics returned to baseline. Serious adverse events in those who received lidocaine occurred in three patients. Their mean arterial blood pressure dropped below 60 and per study protocol, required intravenous ephedrine to increase it. This was limited to when patients were intubated. Outside of that time period, no patients who received lidocaine had any serious adverse events.

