5.2 Safety Evaluation

Subject safety will be monitored by serious adverse events, reported adverse events, vital signs, physical examinations, laboratory data (obtained through standard care), and medications required to treat any adverse events thought to be due to the study drug. In the event of any serious adverse event, a lidocaine level will be drawn on the patient.

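### The SAE definition in 8.4 has no criterion for an important event reversed by treatment, so such events could be left out of the SAE endpoint and the only numerical safety boundary

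*Combined protocol and SAP*

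**What the plan says.** **Definition.** Section 8.4 begins "An SAE is any untoward medical occurrence that" and lists five outcomes. Two could apply to an acute drug reaction that the patient survives without lasting harm: the event "is life-threatening", or it "requires inpatient hospitalization or prolongation of existing hospitalization". Section 8.4 does not define the first of these further.

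**Evidence review.** Section 1.2.2.2, on a cited cardiac-surgery trial of lidocaine, states: "Serious adverse events in those who received lidocaine occurred in three patients". It then describes the events: "Their mean arterial blood pressure dropped below 60 and per study protocol, required intravenous ephedrine to increase it". The same section goes on to say that this trial had the highest rate of serious adverse events among those reviewed. Section 1.2.2.1 describes what appear to be the same events as side effects, with a pressure threshold of 65 instead of 60.

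**Uses of SAE status.** The safety boundary in 6.4 is met if the chi-square P-value for the "difference between groups in the serious adverse event outcome is 0.025 or less". Section 5.2 adds: "In the event of any serious adverse event, a lidocaine level will be drawn on the patient". SAE status also defines one of the between-arm comparisons in 6.2, two of the three rows in the reporting table of 8.5, and one ground on which the DSMB may ask for unblinded data (9.1.3).

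**The concern.** The protocol uses the word serious in one way when it reviews other trials and, on a strict reading, more narrowly when it counts its own events. The setting makes the difference matter. Patients are dosed in an emergency department, on a cardiac monitor (9.4.2), with cardiac drugs, defibrillators, naloxone and ventilation equipment at hand (8.7). The protocol discusses arrhythmia (1.2.2.2, 9.4.2), hypotension (1.2.2.1, 1.2.2.2) and, for hydromorphone, respiratory depression (3.1.2); a history of seizures is an exclusion (3.5.2). Events of these kinds can be reversed on the spot.

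At stake is the one safety rule with a number attached. If reversed events are classified as non-serious, an imbalance between arms in such events would not enter the test in 6.4. A report of few or no SAEs would then rest on a narrower meaning of the term than the one used in 1.2.2.2. The lidocaine level is a further loss, because a sample not drawn at the time cannot be recovered if the event is reclassified later.

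**Working it through.** **1. The plan's own figures.** The plan gives no expected SAE rate and no operating characteristics for the safety boundary, so there is no figure on this point to reproduce. Its sample size (6.3) does not depend on the SAE definition and reproduces: 2 × (1.960 + 0.842)² × 3² / 1.3² = 83.6, so 84 per arm; the t-test version gives 84.6, so 85; 170 × 1.10 = 187.

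**2. Applying 8.4 to a reversed event.** Take hypotension corrected with a drug, with no sequelae.

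| Criterion in 8.4 | Met? |
|---|---|
| Death | No |
| Threat to life | Depends on a clinician's judgement; no guidance given |
| Admission or longer stay | Only if the event itself causes it |
| Lasting disability | No |
| Birth defect | No |

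If both conditional rows are answered no, the event is not an SAE. The need for treatment does not enter the definition.

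**3. The boundary at the interim look.** Inputs: 94 enrolled and P ≤ 0.025 by chi-square (6.4); allocation roughly 50/50 (3.2), so 47 per arm is assumed. Section 6.4 does not say whether a continuity correction is used, so both forms are shown. With x events on lidocaine and 0 on hydromorphone, the 2 × 2 statistic reduces to:

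- uncorrected: X² = 94x / (94 − x)
- corrected: X² = 94(x − 1)² / [x(94 − x)]

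| x v 0 | Uncorrected X², P | Corrected X², P |
|---|---|---|
| 4 v 0 | 376/90 = 4.18, 0.041 | P = 0.125 |
| 5 v 0 | 470/89 = 5.28, **0.0216** | P = 0.066 |
| 6 v 0 | P = 0.0114 | 2350/528 = 4.45, 0.0349 |
| 7 v 0 | 658/87 = 7.56, 0.0060 | 3384/609 = 5.56, **0.0184** |

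The boundary is first met at 5 v 0 uncorrected and at 7 v 0 corrected. With one hydromorphone event it needs 8 v 1 (P = 0.0141) or 9 v 1 (P = 0.0192) respectively.

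**4. Chance of crossing if every such event counted.** Binomial counts, 47 per arm, no hydromorphone events, lidocaine rates assumed:

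| Assumed lidocaine rate | Uncorrected | Corrected |
|---|---|---|
| 5% | 8.5% | 0.8% |
| 10% | 51% | 19% |
| 15% | 85% | 57% |
| 30% | >99% | 99.5% |

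The 30% row matches the 3 of 10 lidocaine patients in the cited trial (exact 95% interval 6.7% to 65.2%) and serves only as an upper marker. If none of these events is classified as an SAE, they contribute nothing to the test at any rate.

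**The case against.** The strongest reply is that the gap is narrow and the events are not lost.

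- **The listed criteria can capture them.** Severe hypotension, or an event needing defibrillation or ventilatory support, would often be judged life-threatening, and some events would lead to admission. This stands: a reader might infer that 8.4 excludes drug-treated hypotension outright, and it does not. It leaves an input to a stopping rule to unguided, case-by-case judgement.
- **They are recorded and compared elsewhere.** New symptoms, vital signs, drugs given for AEs, naloxone and changes of disposition are recorded at every timed assessment after dosing (4.2). Drug-treated AEs, naloxone and disposition changes are compared between arms (6.2), AEs are summarized by type (6.2.4), and each AE is graded for intensity and causality (8.3). This stands too: a cluster would be visible. But no boundary is attached to those endpoints, and the drug-treated-AE endpoint also counts treatment of minor effects.
- **Prompt reporting has a second route.** A reader might infer that such events would escape prompt reporting altogether. Sections 8.2 and 8.5 do not support that: an unanticipated problem is reported within 5 days whether or not it is an SAE. Because the protocol itself discusses hypotension and arrhythmia, such an event may not qualify as unanticipated; a notable non-serious AE then waits for continuing review (8.2).
- **The cited trial is an outlier.** It used 3 mg/kg in cardiac-surgery patients who also received fentanyl, morphine and lorazepam, and the protocol says so (1.2.2.2). The study on which this trial builds is the group's earlier emergency department trial (1.2), which reported no SAEs. The 3 of 10 is therefore not a forecast. It shows only that the word serious is used inconsistently, and since 1.2.2.1 calls apparently the same events side effects, the protocol has no settled wider definition either.
- **Part of the safety system is out of view.** Stopping rests primarily with the DSMB (6.4), whose procedure is in the IND application (9.4.1), and IRB reporting follows an attachment. Neither is available here, so further triggers can be neither confirmed nor ruled out.

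**Conclusion.** The point holds in a limited form. The list in 8.4 is closed and has no criterion for an important event reversed by treatment, while 1.2.2.2 calls such events serious. A transient, treated event that is neither judged life-threatening nor a cause of admission or a longer stay could be left out of the SAE comparison, the only numerical safety boundary and the SAE reporting clocks, and would not prompt a lidocaine level.

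On size: with 47 per arm and no hydromorphone events, five to seven classifications can decide whether the boundary is met. That rests on an assumed even split, an unstated choice of continuity correction, and illustrative counts that the documents do not support as expected rates. A result of 0 v 0 despite several treated events requires every one of them to fall outside both the life-threatening and the hospitalization criteria.

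This is a cheap improvement. It leaves the primary analysis and sample size unaffected and does not show that patients would go unmonitored.

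**What to change.** 1. Add one criterion to 8.4: an event that needs medical intervention to prevent one of the outcomes already listed.
2. State before the interim look which reversed events count, for example drug-treated hypotension or arrhythmia, seizure, and respiratory depression needing reversal. Add a tick box to the case report form.
3. Apply the definition blinded and identically in both arms, for 6.2, 6.4 and 8.5.
4. Reconcile 1.2.2.1, 1.2.2.2 and 8.4 on whether drug-treated hypotension is serious, including the two pressure thresholds (65 and 60) given for apparently the same events.
5. State whether the lidocaine level in 5.2 follows the wider definition; that is for the sponsor to decide.

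The cost is a short amendment, a few more SAE reports and possibly more blood draws. The boundary also changes character. It tests for a difference in either direction, so events reversed with naloxone on hydromorphone would count and could offset lidocaine events: 7 v 0 meets it in both forms of the test, whereas 7 v 1 does not (P = 0.0266 uncorrected, 0.0646 corrected). The DSMB should know this before it uses the rule and should see SAEs broken down by type alongside the test.
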